4.2.1.2 Prevention/management strategies for diarrhea

Diarrhea can be a common side effect of regorafenib. The preventive/management strategies for diarrhea should be consistent with local standards (e.g., anti-diarrheas and optimized hydration status). Anti-diarrhea medications may be introduced if symptoms occur. Previous trials have shown that the diarrhea could be managed with loperamide. The recommended dose of loperamide is 4 mg at first onset, followed by 2 mg every 2 to 4 hours until diarrhea-free for 12 hours.

4.3 Concomitant Medications/Treatments

All medication that is considered necessary for the subject's welfare, and which is not expected to interfere with the evaluation of the study treatment, may be given at the discretion of the investigator. All medications (including contrast media) taken within 2 weeks prior to the start of the study and during the study must be recorded in the subject's source documentation and in the CRF (including start/stop dates, dose frequency, route of administration, and indication). Specific caution should be taken when considering or administering a concomitant medication that is metabolized by the cytochrome enzymes CYP2C8, CYP2B6 and CYP2C9. Such concomitant medication should be

avoided, if possible.

Co-administration of a strong CYP3A4 inducer (rifampin) with a single 160 mg dose of Stivarga decreased the mean exposure of regorafenib, increased the mean exposure of the active metabolite M-5, and resulted in no change in the mean exposure of the active metabolite M-2. Avoid concomitant use of Stivarga with strong CYP3A4 inducers (e.g. rifampin, phenytoin, carbamazepine, phenobarbital, and St. John's Wort)

Co administration of a strong CYP3A4 inhibitor (ketoconazole) with a single 160mg dose of regorafenib increased the mean exposure of regorafenib and decreased the mean exposure of the active metabolites M-2 and M-5. Avoid concomitant use of Stivarga with strong inhibitors of CYP3A4 activity (e.g. clarithromycin, grapefruit juice, itraconazole, ketoconazole, nefazadone, posaconazole, telithromycin, and voriconazole).

Permitted concomitant therapy includes:

- Standard therapies for concurrent medical conditions.
- Supportive care for any underlying illness.
- Palliative radiation therapy is allowed if the target lesion(s) are not included within the radiation field and no more than 10% of the bone marrow is irradiated.
- Granulocyte colony-stimulating factor (G-CSF) and other hematopoietic growth factors may be used in the management of acute toxicity, such as febrile neutropenia, when clinically indicated or at the investigator's discretion. However, they may not be substituted for a required dose reduction. Subjects are permitted to take chronic erythropoietin.
- Treatment with nonconventional therapies (such as acupuncture), and vitamin/mineral supplements are permitted provided that they do not interfere with the study endpoints, in the opinion of the investigator.
- Bisphosphonates
- Octreotide
- Subjects who are therapeutically treated with an agent such as warfarin or heparin will be allowed to participate provided that their medication dose and INR/PTT are stable. Close monitoring (day 5 of cycle 1 and day 1 of each cycle) is mandatory. If either of these values are above the therapeutic range, the doses should be modified and the assessments should be repeated weekly until they are stable.

The following are not permitted:

- Other investigational treatment during or within 30 days before starting study treatment
- Systemic antitumor therapy, including cytotoxic therapy, signal transduction inhibitors, immunotherapy, and hormonal therapy
- Bone marrow transplant or stem cell rescue
- Subjects taking narrow therapeutic index medications should be monitored proactively (e.g. warfarin, phenytoin, quinidine, carbamazepine, Phenobarbital, cyclosporin, and digoxin). Warfarin is metabolized by the cytochrome enzyme CYP2C9 and it's levels may be

especially affected by regorafenib

- Use of any herbal remedy (e.g. St. John's wort [*Hypericum perforatum*])

4.4 Duration of Therapy

In the absence of treatment delays due to adverse events, treatment may continue until:

- Disease progression
- Inter-current illness that prevents further administration of treatment
- Unacceptable adverse event(s)
- Patient decides to withdraw from the study, **OR**
- General or specific changes in the patient's condition that render the patient unacceptable for further treatment in the judgment of the investigator.

4.5 Removal of Patients from Protocol Therapy

Patients can be taken off the study treatment and/or study at any time at their own request, or they may be withdrawn at the discretion of the investigator for safety, behavioral or administrative reasons. The reason(s) for discontinuation of treatment will be documented and may include:

- Patient withdraws consent (follow-up);
- Patient is unable to comply with protocol requirements;
- Patient demonstrates disease progression (unless continued treatment with study drug is deemed appropriate at the discretion of the investigator);
- Patient experiences toxicity that makes continuation in the protocol unsafe;
- Treating physician determines continuation on the study would not be in the patient's best interest;
- Patient becomes pregnant (pregnancy to be reported along same timelines as a serious adverse event);
- Development of second malignancy (except for basal cell carcinoma or squamous cell carcinoma of the skin) that requires treatment, which would interfere with this study;
- Lost to follow-up. If a research subject cannot be located to document survival after a period of 2 years, the subject may be considered "lost to follow-up." All attempts to contact the subject during the two years must be documented in CRF's.

4.6 Duration of Follow Up

Patients will be followed with phone calls every 3 months until death after removal from treatment. Patients removed from treatment for unacceptable adverse events will be followed until resolution or stabilization of the adverse event.

5.0 STUDY PROCEDURES

5.1 Screening/Baseline Procedures

Assessments performed exclusively to determine eligibility for this study will be done only after obtaining informed consent. Assessments performed for clinical indications (not exclusively to determine study eligibility) may be used for baseline values even if the studies were done before informed consent was obtained.

All screening procedures must be performed within 7 days prior to registration for labs, 28 days for scans unless otherwise stated. The screening procedures include:

- 5.1.1 Medical history. Complete medical and surgical history, history of infections.
- 5.1.2 Demographics. Age, gender, race, ethnicity
- 5.1.3 Review subject eligibility criteria
- 5.1.4 Review previous and concomitant medications
- 5.1.5 Physical exam including vital signs (temperature, pulse, respirations, blood pressure), height, weight
- 5.1.6 SWOG Performance status
- 5.1.7 Adverse event assessment
Baseline adverse events will be assessed. See section 6 for Adverse Event monitoring and reporting.
- 5.1.8 Hematology, coagulation
- 5.1.9 Blood draw for correlative studies:
Two purple top tubes to the [name] lab, See Section 9.0 for details.
- 5.1.10 Serum chemistries: Phosphorus, Magnesium, LDH and Comprehensive metabolic panel (CMP) to include: albumin, alkaline phosphatase, ALT/SGPT, AST/SGOT, BUN, creatinine, electrolytes (sodium, potassium, calcium, chloride, bicarbonate), glucose, and total bilirubin.
- 5.1.11 Urine Pregnancy test (for females of child bearing potential)
- 5.1.12 Tumor assessment
- 5.1.13 Thyroid Function (TSH, T3, T4), 5HIAA, Lipase
- 5.1.14 EKG
- 5.1.15 Serum Chromogranin
- 5.1.16 Ocreotide scan
- 5.1.17 Urinalysis for proteinuria
- 5.1.18 Archival tumor tissue
- 5.1.19 CXR if CT of chest is not done

5.2 Procedures During Treatment**5.2.1 Prior to Each Treatment Cycle**

- Physical exam including vital signs (temperature, pulse, respirations, blood pressure), height, weight
- Hematology
- Concomitant medications
- Urine pregnancy test (if woman of childbearing potential)
- EKG, PT/PT-INR, PTT, Thyroid Function (TSH, T3, T4) if clinically indicated
- SWOG performance status
- Urinalysis for proteinuria
- Serum chemistries: Phosphorus, Magnesium, LDH and Comprehensive metabolic panel (CMP) to include: albumin, alkaline phosphatase, ALT/SGPT, AST/SGOT, BUN, creatinine, electrolytes (sodium, potassium, calcium, chloride, bicarbonate), glucose, and total bilirubin.
- Adverse event evaluation
- 5HIAA
- Pill Diary
- Lipase

5.2.2 Day 8, 15 and 22 of Cycle 1 and 2 only

- BP Monitoring
- Liver Function Tests

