4.2.1.1 Dose Levels and Reductions

Study medication will be administered on a 3 weeks on/1week off schedule [3 weeks out of every 4]. A new cycle of therapy can start when all toxicities, (except hand-foot syndrome, alopecia, non-refractory nausea/vomiting, non-refractory hypersensitivity and nonclinical and asymptomatic laboratory abnormalities) have resolved to Grade 2 or less. Hand-foot syndrome must have resolved to Grade 0-1.

Doses will be delayed or reduced for clinically significant hematologic and non-hematologic toxicities that are related to protocol therapy according to the guidelines shown in the Dose Delays/Dose Modifications table that follows. Dose modifications will follow predefined dose levels. Dose adjustments for hematologic toxicity are based on the blood counts obtained in preparation for the day of treatment.

Strictly follow the modification in the following tables for the first **two** cycles until individual treatment tolerance can be ascertained. Thereafter, these modifications should be regarded as guidelines to produce mild-to-moderate, but not debilitating, side effects. If multiple adverse events are seen, administer dose based on greatest reduction required for any single adverse event observed. Reductions or increases apply to treatment given in the preceding cycle and are based on adverse events observed since the prior dose.

Dose Level			If no SDRT	If + SDRT**
Dose level 0*	80 mg po qd	Two 40-mg tablets of regorafenib	Proceed to next dose level	
Dose level 1	120 mg po qd	Three 40-mg tablets of regorafenib	Proceed to next dose level	Decrease to 80 mg
Dose level 2	160 mg po qd	Four 40-mg tablets of regorafenib		Decrease to 120 mg
* Starting Dose				
** SDRT= Significant Drug Related Toxicities				

If a subject experience more than one toxicity, dose reduction should be according to the toxicity with the highest grade

In the case of two or more toxicities of the same grade, the investigator may dose reduce according to that deemed most causally related to study treatment

The following tables outline dose adjustments for toxicities related to study drug except hand-foot skin reaction, hypertension and liver function test abnormalities.

NCI-CTCAE v4.0 ^a	Dose Interruption	Dose Modification ^b	Dose for Subsequent Cycles
Grade 0-2	Treat on time	No change	No change

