- Keratolytic creams (e.g. urea-based creams, salicylic acid 6%) may be used sparingly and only to affected (hyperkeratotic) areas.
- Alpha hydroxyl acids (AHA) based creams may be applied liberally 2 times a day. Approximately 5% to 8% provides gentle chemical exfoliation.
- Topical analgesics (e.g. lidocaine 2%) are to be considered for pain control.
- Topical corticosteroids like clobetasol 0.05% should be considered for subjects with Grade 2 or 3 HFSR. Avoid systemic steroids.

Tender areas should be protected as follows:

- Use socks/gloves to cover moisturizing creams
- Wear well-padded footwear
- Use insole cushions or inserts (e.g. silicon, gel)
- Foot soaks with tepid water and Epson salts

Hypertension

Hypertension is a known AE associated with regorafenib treatment. Subject will have their blood pressure measured at least weekly at the study site during the first 6 weeks of treatment. If additional blood pressure measurements are done outside the study site, and the blood pressure is > 140 mm Hg systolic or > 90 mm Hg diastolic (NCI CTCAE v4.0), then the subject must contact study personnel. The management of hypertension, including the choice of antihypertensive medication, will be performed according to local standards and to the usual practice of the investigator. Every effort should be made to control blood pressure by medical means other than study drug dose modification. If necessary, Table 4 outlines suggested dose reductions.

Table 4: Management of Treatment-Emergent Hypertension		
Grade of event (CTCAE v4.0)	Antihypertensive Therapy	Regorafenib Dosing
Grade 1 Prehypertension (systolic BP 120 - 139 mmHg or diastolic BP 80 - 89 mmHg)	None	
 • Continue regorafenib • Consider increasing blood pressure (BP) monitoring

Grade 2 Systolic BP 140 - 159 mmHg or diastolic BP 90 - 99 mmHg, OR Symptomatic increase by > 20 mmHg (diastolic) if previously within normal limits
	
 • Treat with the aim to achieve diastolic BP \leq 90 mm Hg: • If BP previously within normal limits, start anti-hypertensive monotherapy • If patient already on anti-hypertensive medication, titrate up the dose. 	
 • Continue regorafenib • If symptomatic, hold regorafenib until symptoms resolve AND diastolic BP \leq 90 mm Hg^a. When regorafenib is restarted, continue at the same dose level.

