5.2.3 Day 15 of all Cycles

- Serum chemistries: Phosphorus, Magnesium, LDH and Comprehensive metabolic panel (CMP) to include: albumin, alkaline phosphatase, ALT/SGPT, AST/SGOT, BUN, creatinine, electrolytes (sodium, potassium, calcium, chloride, bicarbonate), glucose, and total bilirubin.
- Hematology

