5.4 Study Calendar

Cycles will be 28 Days. Regorafenib will be taken orally Days 1-21 of each Cycle. For first cycle all labs and EKG should be done within 7 days of first receiving study drug. For the first cycle, Imaging studies should be done within 28 days of first receiving study drug.

Parameter	Pre-Treatment ⁶	Day 1 of All Cycles ¹ ²	Day 8, Day 15 And 22 of Cycle 1 and 2 only ¹²	Day 15 of all Cycles ¹ ²	One Day of Week 3 Of every other Cycle (starting with Cycle 2)	Off study	Follow-up
Informed Consent	X						
Pill Diary		X				X	
History & Physical Exam	X	X					
Weight, SWOG Performance Status, Con Meds	X	X				X	
Adverse Event/Toxicity Evaluation	X	X					
WBC (differential), Hgb, Platelets	X	X		X			
Complete Metabolic Panel, Phosphorus, Magnesium, LDH	X	X	Liver function	X			
Lipase	X	X					
Thyroid Function (TSH, T3, T4)	X	X ³					
PT/PT-INR, PTT	X	X ^{3,9}					
Urinalysis for proteinuria	X	X					
5HIAA	X	X					
Serum Chromogranin	X				X		
Octreotide scan	X				Cycle 2 only		
EKG	X	X ³					
CXR (if CT of chest not done)	X ⁷				X ⁷		
BP Monitoring		X	X				
Radiology, x-ray or Scans for disease measurement ²	X ⁸				X		X ¹⁰
Archival tumor tissue	X ⁸						
Plasma	X ⁸					X ⁸	
Urine Pregnancy Test	X ⁵	X ⁵					
Survival Follow-up							X ¹¹

- 1 If used to follow measurable disease.
- 2 Within 28 days of Cycle 1, Day 1.
- 3 As clinically indicated.
- 4 Paraffin embedded tissue must be available for review.
- 5 For women of childbearing potential
- 6 Confirm response within 4 weeks.
- 7 Not required if CT scan of the chest is done.
- 8 See section 9. For plasma two purple top tubes to the [name] lab.
- 9 Close monitoring (day 5 of cycle 1 and day 1 of each cycle) of PT/PT-INR and PTT is mandatory for patients on agents such as warfarin and heparin.
- 10 Patients that come off for reasons other than disease progression will have their standard of care scans measured via RECIST until progressive disease, to determine date of disease progression
- 11 Patients will be followed up via phone call, medical records or database search until death to determine survival time
- 12 All study visits allow a +/- 7 day window

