Tumor response rate will be calculated as a proportion of patients who have either a complete or partial response among all patients in the primary data analysis set. The 95% confidence intervals will be given.

OS will be analyzed in the same way as PFS.

Toxicity profile will be summarized by attribution: regorafenib-related and all reported, course: cycle 1 and all cycles, type, and grade: grade 1-2, 3-4, and 5.

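### From Cycle 3 no on-drug blood pressure reading is scheduled, so the all-cycles toxicity summary pools cycles with unequal detection of hypertension

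*Combined protocol and SAP*

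**What the plan says.** All references are to the combined protocol and SAP.

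- **Dosing.** Section 4.2.1.1: "Study medication will be administered on a 3 weeks on/1week off schedule". Section 5.4: "Cycles will be 28 Days. Regorafenib will be taken orally Days 1-21 of each Cycle".
- **Pre-cycle visit.** Section 5.2.1, headed "Prior to Each Treatment Cycle", lists "Physical exam including vital signs (temperature, pulse, respirations, blood pressure), height, weight". The calendar in 5.4 places this visit on Day 1 of all cycles, and its footnote 12 gives every visit a window of 7 days either way.
- **Extra BP readings.** These belong to the visits headed "5.2.2 Day 8, 15 and 22 of Cycle 1 and 2 only". The hypertension text in 4.2.1.1 fits with this: "Subject will have their blood pressure measured at least weekly at the study site during the first 6 weeks of treatment". It also obliges patients to report an off-site reading above 140 systolic or 90 diastolic. That duty has no end date, but off-site readings are not themselves required.
- **Other visits during dosing.** The visit headed "5.2.3 Day 15 of all Cycles" lists serum chemistries and hematology only. The week 3 visit in every other cycle (5.2.4, 5.2.5) lists chromogranin, tumor assessment and, in Cycle 2, an octreotide scan. Neither includes BP.
- **Where hypertension is used.** Table 4 in 4.2.1.1 ties action to the grade of hypertension, with no limit by cycle. Section 7.5 counts unacceptable toxicity in any course. Section 10.3 summarizes toxicity by attribution and by "course: cycle 1 and all cycles, type, and grade: grade 1-2, 3-4, and 5".

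**The concern.** Hypertension is named in 4.2.1.1 as a known effect of the drug and has its own management table. The protocol looks for it on drug in Cycles 1 and 2 and then stops scheduling on-drug readings, although treatment, Table 4 and the section 7.5 count all continue. The visit that is on drug in every cycle (Day 15) already takes place but does not record BP. Liver tests, by contrast, keep an on-drug measurement in every cycle because they are part of the Day 15 chemistries.

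What is at stake is how far the safety results can be interpreted. Toxicity is a stated secondary objective (2.2.2). A figure for all cycles that mixes closely watched cycles with cycles in which no on-drug reading is scheduled does not have one consistent meaning. If later hypertension looks uncommon, a reader cannot tell whether it was absent or not looked for. Two rules also use later-cycle BP. Footnote b of Table 4 makes dose re-escalation depend on BP having been controlled for at least one cycle. Section 7.5 counts Grade 3 non-hematologic events that do not return to Grade 1 or less within 96 hours, in any course.

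**Working it through.** The plan gives no figure of its own on this point. The check is a count of visits and dosing days.

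**Inputs.** 28-day cycles with dosing on Days 1–21 (5.4). BP before each cycle (5.2.1) and on Days 8, 15 and 22 of Cycles 1–2 (5.2.2). Landmark at Day 182 (6.1.10). Assumptions: nominal visit days, no dose delays, study Day 1 is the first dose, and the pre-cycle reading precedes that day's dose.

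**Study day** = 28 × (cycle − 1) + cycle day.

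| Cycle | Pre-cycle BP (study day) | Days 8 and 15, on drug | Day 22, off drug |
|---|---|---|---|
| 1 | 1 (before any drug) | 8, 15 | 22 |
| 2 | 29 | 36, 43 | 50 |
| 3 | 57 | none | none |
| 4 | 85 | none | none |
| 5 | 113 | none | none |
| 6 | 141 | none | none |
| 7 | 169 | none | none |

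**On-drug readings.** There are four, on study days 8, 15, 36 and 43. The Day 22 readings come one day after the last dose (Day 21), so they are not on drug, though they are close to it.

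**Gap before the pre-cycle reading.** 28 − 21 = 7 drug-free days. With the window, a visit 7 days early falls on Day 29 − 7 = Day 22 of the preceding cycle, one day after the last dose. The gap therefore ranges from 0 to 7 full days for an on-time or early visit. A visit held before the cycle, as 5.2.1 requires, and inside the early side of the window is still off drug.

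**Dosing days through Day 182.** Six full cycles end on Day 6 × 28 = 168. Cycle 7 starts on Day 169 and contributes 182 − 168 = 14 dosing days.

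- Total: 6 × 21 + 14 = 140.
- Cycles 1–2: 2 × 21 = 42.
- Cycles 3–7: 140 − 42 = 98, and 98 / 140 = 70%.
- Cycles begun with no scheduled on-drug BP: 5 of 7.

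**Against the section 7.5 definition.** 96 hours is 4 days, shorter than the nominal 7-day gap. A Grade 3 rise on drug in Cycle 3 or later could last beyond 96 hours, and so qualify, yet settle before the next scheduled reading. Rises that settle within 96 hours are excluded by definition, and Grade 2 rises never count.

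**Urine protein and lipase.** During treatment both are listed only at the pre-cycle visit, so neither is ever scheduled on drug, in any cycle.

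**The case against.** The strongest reply is that late hypertension is not invisible. Off-site readings above 140/90 must be reported at any time. Adverse events and concomitant medications are reviewed before every cycle, and section 4.3 requires drugs to be recorded with their indication, so a new antihypertensive would show. Vital signs are taken at the off-study visit. A rise that lasts through the off week is caught by the pre-cycle reading. All of this stands. A reader might infer that on-drug hypertension can be recorded only in Cycles 1–2; the documents do not support that. What is confined to those cycles is the scheduled on-drug reading. Off-site readings are optional, and questioning a patient will not reveal a silent rise.

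A reader might also infer that Table 4 works only on measured BP. It does not: Grade 3 includes a need for more than one drug or more intensive therapy, and Grade 4 is defined by life-threatening consequences. Section 4.2.1.1 also treats the modification tables as guidelines once the first two cycles are over. Table 4 is thus weakened by missing readings, not disabled.

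Nor do the documents support saying that recorded hypertension must fall over time or that the safety profile will look too favorable. They give no time course of BP after the last dose, and section 10.3 plans no cycle-by-cycle trend; its all-cycles figure includes Cycles 1–2. What remains is that the pooled figure combines unequal detection without saying so.

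Finally, early concentration of monitoring is a deliberate choice, and the 6-week rule and the Cycle 1–2 visits agree with each other. That is fair. The mismatch is between that schedule and the rules and summaries that run through every cycle.

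**Conclusion.** The point holds in a limited form. On nominal days, on-drug BP is scheduled four times, all in Cycles 1–2. Through Day 182, 70% of dosing days fall in later cycles with none. From Cycle 3 the recording of hypertension rests on unscheduled detection or on a rise that outlasts the off week, so the section 10.3 summary and the section 7.5 count pool cycles with unequal detection.

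The likely direction is an under-count of later hypertension. This assumes that at least some rises settle during the off week, which the documents neither state nor exclude. The size cannot be computed from them. The day counts assume nominal visits and no delays; the ±7-day window shifts individual readings but adds no on-drug reading by design.

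It would be wrong to carry this over to the efficacy design. Exact calculation gives type I error 0.0514 and power 0.805 for cohort A, and 0.0531 and 0.801 for cohort B, in line with the stated 5.1%, 5.3% and 80%. The section 7.5 rule gives 0.794 at a 33% toxicity rate and 0.029 at 10%, against the stated 0.79 and 0.030. Those last figures refer to the true rate and so take every qualifying event as observed.

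The urine protein and lipase schedule is worth noting but is weaker ground: asymptomatic laboratory abnormalities are excluded from the general dose-modification table (note b). This is a cheap improvement to a descriptive secondary objective, not a flaw in the primary analysis.

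**What to change.** 1. **Reconcile the schedule with its uses.** The BP provisions in 4.2.1.1 (hypertension), 5.2.2, 5.2.3 and 5.4 should be brought into line with Table 4 and section 7.5, which apply in all cycles. One way is to record BP as a safety-data item at the Day 15 visit, which already takes place on drug in every cycle. The cost is a calendar amendment, a slightly longer visit and possibly a higher recorded hypertension rate.
2. **Amend section 10.3.** Tabulate hypertension by cycle, showing for each cycle the number of patients who had an on-drug reading. State that ascertainment differs between Cycles 1–2 and later cycles. This costs one table and one sentence, and is worth doing even if the calendar stays as it is.
3. **Urine protein and lipase.** State in the safety report that neither was scheduled on drug. No added tests are asked for.

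No dose, treatment or stopping rule is proposed; how Table 4 is applied remains for the sponsor and investigators.
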